7.6 Secondary Efficacy Endpoint measures

In order to assess the correlation of MBT with other measures of liver disease the following endpoint measures will be collected:

| | |
|---|---|
| Exalenz Bioscience Ltd. | Last update: February 20, 2018 |
| Study Title: Companion protocol for the ¹³C-Methacetin Breath Test (MBT) for use in Bristol-Myers Squibb phase 2b studies for BMS-986036 (PEG-FGF21), under Protocols MB130-068 and MB130-069 | Protocol: BMS-EX-0118 Version: 1.0 |
| Document No: CSP000002 | Page 22 of 38 |

For all study cohorts: MBT results for each MBT visit (day 1, week 24, week 48,) as well as changes in MBT results (CPDR30/PDR peak or other breath test parameters).

The other measures of liver disease that will be collected in this study are as follows:

Liver Fibrosis stage and NAS as determined by Liver Biopsy, PDFF as determined by MRI where available, Liver Stiffness as determined by MRE where available, Serum Biomarker Pro-C3

Additional measures for cohort 2: MELD and CTP scores, Liver Stiffness as determined by Fibroscan® Elastography, Liver-related Clinical Outcome defined as the first occurrence of any one of the following: all-cause mortality, MELD score ≥ 15 , liver transplant, hepatocellular carcinoma (HCC), ascites requiring medical intervention, hospitalization (≥ 24 hours) for onset of variceal bleed, hepatic encephalopathy, spontaneous bacterial peritonitis.

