7.7 Efficacy Variables

Study procedures and timing are summarized in the Schedule of Events of protocols MB130-068 and MB130-069.

The following procedures or tools will be used to assess subjects' disease activity during the study:

- MBT at selected sites in subjects who opt in at Day 1, week 24 and week 48.
- Liver biopsy at Screening (if no biopsy is available from within 6 months of the Screening Visit), week 24 (for subjects in protocol MB130-068/cohort 1) or week 48 (for subjects in protocol MB130-069/cohort 2)
 - Histological assessments of fibrosis stage and NASH activity (NAS)
- Liver stiffness as determined by MRE at selected sites at screening, week 24 and week 48
- Hepatic fat fraction as determined by MRI at selected sites at screening, week 24 and week 48.
- Serum Biomarker Pro-C3 at Screening, Day 1, week 24, week 48 and week 52.

Additional variables for cohort 2:

- Fibroscan® elastography at Screening and week 48 or early termination
- MELD Scores at Screening, Day 1, every 4 weeks up to week 24, every 8 weeks up to week 48 and week 52.

| | |
|---|---|
| Exalenz Bioscience Ltd. | Last update: February 20, 2018 |
| Study Title: Companion protocol for the ¹³C-Methacetin Breath Test (MBT) for use in Bristol-Myers Squibb phase 2b studies for BMS-986036 (PEG-FGF21), under Protocols MB130-068 and MB130-069 | Protocol: BMS-EX-0118 Version: 1.0 |
| Document No: CSP000002 | Page 23 of 38 |

- Child-Pugh scores at Screening, Day 1, every 4 weeks up to week 24 and every 8 weeks up to week 48 and week 52.
- Liver-related Clinical outcome events at each visit from Day 1 through week 52 and during the Long-Term Bone Mineral Density and Immunogenicity Follow-Up Period (up to 14 Months after week 52).

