7.7.1.1 Histological Assessments

The NASH Clinical Research Network (CRN) system will be used to score the histologic samples. The NASH CRN system is based on the concept that necro-inflammatory lesions and stage of fibrosis should be evaluated separately; it assesses liver biopsies for degree of steatosis (0-3), lobular inflammation (0-3), hepatocellular ballooning (0-2), and fibrosis (0-4). The first 3 components are added together in an unweighted fashion to determine the NASH activity score (NAS) that ranges from 0 to 8. Fibrosis is staged separately on a 0-4 scale: 0 (none); 1 (perisinusoidal or periportal); 2 (perisinusoidal and portal/periportal); 3 (bridging fibrosis); 4 (cirrhosis). It should be noted, the NAS should not be considered a replacement for a pathologist's diagnosis of NASH.

Table 1 NAS Scoring System

| Histology Variable | Grade | Score |
|-----------------------------------|----------|-------|
| Steatosis Grade | < 5% | 0 |
| | 5-33% | 1 |
| | > 33-66% | 2 |
| | >66% | 3 |
| Lobular Inflammation ^a | none | 0 |

| | |
|---|---|
| Exalenz Bioscience Ltd. | Last update: February 20, 2018 |
| Study Title: Companion protocol for the ¹³C-Methacetin Breath Test (MBT) for use in Bristol-Myers Squibb phase 2b studies for BMS-986036 (PEG-FGF21), under Protocols MB130-068 and MB130-069 | Protocol: BMS-EX-0118 Version: 1.0 |
| Document No: CSP000002 | Page 24 of 38 |

| Histology Variable | Grade | Score |
|---------------------------|--------------|--------------|
| | < 2 | 1 |
| | 2-4 | 2 |
| | > 4 | 3 |
| Ballooning | none | 0 |
| | few | 1 |
| | many | 2 |

^a foci per x200 field

Liver biopsy samples will be used by the site to assess NASH and fibrosis stage as per the site's standard practice.

7.7.2 *Clinical Outcome Events*

Cohort 2 will be evaluated for the following liver-related clinical outcome events at every visit during the treatment periods:

- All-cause mortality
- MELD score ≥ 15 (with at least a 2-point increase from Baseline)
- Liver transplant
- Ascites requiring medical intervention
- Hospitalization (≥ 24 hours) for onset of variceal bleed
- Hospitalization (≥ 24 hours) for hepatic encephalopathy
- Hospitalization (≥ 24 hours) for spontaneous bacterial peritonitis
- HCC

7.7.3 *Magnetic Resonance Elastography (MRE)*

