7.7.7 MELD Scoring

MELD scoring, to be performed for cohort 2 (see Appendix 10 of study protocol MB130-069) is a score for assessing the severity of chronic liver disease that does not include subjective variables such as ascites and encephalopathy. It employs the subject's bilirubin, serum creatinine, and prothrombin time (INR).

Blood samples will be taken for bilirubin, serum creatinine, and prothrombin time as part of the hematology and serum chemistry assessments conducted at each visit. The same central laboratory will be used for each evaluation. The central laboratory will calculate the

| | |
|---|---|
| Exalenz Bioscience Ltd. | Last update: February 20, 2018 |
| Study Title: Companion protocol for the ¹³C-Methacetin Breath Test (MBT) for use in Bristol-Myers Squibb phase 2b studies for BMS-986036 (PEG-FGF21), under Protocols MB130-068 and MB130-069 | Protocol: BMS-EX-0118 Version: 1.0 |
| Document No: CSP000002 | Page 27 of 38 |

MELD score based on the laboratory values and communicate the score to the site. MELD scores will be determined at each study visit.

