1. Liver-related Clinical Outcome defined as the first occurrence of any one of the following: all-cause mortality, MELD score ≥ 15 , liver transplant, hepatocellular carcinoma (HCC), ascites requiring medical intervention, hospitalization (≥ 24 hours) for onset of variceal bleeding, hepatic encephalopathy and spontaneous bacterial peritonitis.
2. Liver Fibrosis stage and NAS as determined by Liver Biopsy assessed by a central reader.
3. Liver Stiffness as determined by MRE.
4. PDFF as determined by MRI.
5. Serum Biomarker Pro-C3.

Meridian Bioscience Israel Ltd.	Last update: May 05, 2021
SAP for Protocol BMS-EX-0118: Companion protocol for the ¹³C-Methacetin Breath Test (MBT) for use in Bristol-Myers Squibb phase 2b studies for BMS-986036 (PEG-FGF21), under Protocols MB130-068 and MB130-069	Document Version: 1.0
Document Nº: CSD00114	Page 11 of 21

Additional measures for cohort 2 include:

1. Liver Stiffness as determined by Fibroscan® Elastography
2. MELD scores
3. CTP scores

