SAP for Protocol BMS-EX-0118: Companion protocol for the ¹³C-Methacetin Breath Test (MBT) for use in Bristol-Myers Squibb phase 2b studies for BMS-986036 (PEG-FGF21), under Protocols MB130-068 and MB130-069	Document Version: 1.0
Document Nº: CSD00114	Page 17 of 21

Day 1 MBT date plus 1). Subjects will be censored at their last study visit for the following reasons:

- If a subject discontinues the study prior to the end of the study without experiencing an event
- If a subject reaches the Final Treatment visit without experiencing an event

Survival analysis will be conducted using the Cox proportional hazard model. The model summary will include the number of subjects in the model, and a table with each covariate in a separate line specifying the coefficient's value, Hazard Ratio, Hazard Ratio 95% Confidence Interval and p-value. In addition, a Kaplan-Meier plot for event-free survival will be presented, stratified by MBT parameter along with the MBT parameter log-rank p-value. Additionally, a crosstab table of MBT parameter and events will be presented.

8.4.2.2 Correlations between changes in MBT parameters and changes in other liver related parameters

Repeat MBT results (cPDR₃₀, PDR_{peak} or other breath test parameters) and their changes in subjects with and without treatment (BMS-986036) for nonalcoholic steatohepatitis (NASH) at Day 1, Week 24 and Week 48 (or Early Termination visits) will be compared and tested for correlation to baseline, as well as repeat results (change from baseline), for the following measurements:

- a. Biopsy based Fibrosis and/or NAS score
- b. Liver stiffness as measured by MRE
- c. PDFF as measured by MRI
- d. Serum Pro-C3 results
- e. Liver elastography by Fibroscan (in cohort 2 only)
- f. MELD scores (in cohort 2 only)
- g. CTP scores (in cohort 2 only)

Linear Regression will be applied in order to test for significance of the correlations between MBT and the liver measurements listed above.

Changes in MBT are measured as the difference between baseline and each of the MBT visits as well as the change in measurements between two subsequent visits in each of the two treatment groups.

Meridian Bioscience Israel Ltd.	Last update: May 05, 2021
SAP for Protocol BMS-EX-0118: Companion protocol for the ¹³C-Methacetin Breath Test (MBT) for use in Bristol-Myers Squibb phase 2b studies for BMS-986036 (PEG-FGF21), under Protocols MB130-068 and MB130-069	Document Version: 1.0
Document Nº: CSD00114	Page 18 of 21

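### The SAP applies a liver outcome containing MELD to both cohorts and leads with the pooled population, although at least its MELD component is planned for cohort 2 only

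*SAP*

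**What the plan says.** **Protocol.** The synopsis and section 7.6 treat the composite as a cohort 2 measure: "Additional measures for cohort 2: MELD and CTP scores, Liver Stiffness as determined by Fibroscan® Elastography, Liver-related Clinical Outcome defined as" and then the component events. Section 7.7 schedules it under the additional variables for cohort 2: "Liver-related Clinical outcome events at each visit from Day 1 through week 52" and on into long-term follow-up. Section 7.7.2 reads "Cohort 2 will be evaluated for the following liver-related clinical outcome events at every visit during the treatment periods", and section 7.7.7 reads "MELD scoring, to be performed for cohort 2". Sections 7.2 and 9.2.2 nevertheless ask for the prognostic assessment in each cohort and in both combined.

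**SAP.** Section 3.2.2 makes the composite, MELD threshold included, item 1 of a list that is not limited by cohort: "Liver-related Clinical Outcome defined as the first occurrence of any one of the following: all-cause mortality, MELD score" of at least 15, and so on. Its separate list, "Additional measures for cohort 2 include", holds only Fibroscan, MELD scores and CTP scores. Section 3.1.2 sets the prognostic objective on the combined population and adds that each cohort will also be reported. Section 8.4.2.1 names no cohort. It specifies a Cox model with site and randomized arm, a Kaplan-Meier plot split by MBT group with a log-rank p-value, and a crosstab of MBT group against events. One of its two reasons for censoring is "If a subject reaches the Final Treatment visit without experiencing an event". Section 2 says that the SAP prevails over the protocol where they differ.

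**The concern.** A composite is one endpoint only if its components are looked for in the same way in everyone analysed. Here the SAP counts a MELD event for cohort 1 but plans to collect MELD in cohort 2 alone. The protocol's limit of the outcome to cohort 2 cannot settle the matter, because the SAP overrides it. A cohort 1 subject without a recorded event enters the risk set and is censored as event-free, when part of the outcome may simply not have been assessed.

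Two outputs are at stake. One is the absolute event risk in the high-risk and lesser-risk MBT groups. The other is the comparison between those groups: if low PDRpeak is commoner in cohort 2, events are sought more fully where the high-risk subjects cluster. The analysis is descriptive, but the documents say the data may be used in future submissions.

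**Working it through.** The documents give no event count, event rate or hazard ratio for this analysis, so there is no figure of the plan to reproduce. The planned sizes are consistent: 160 + 100 = 260.

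**1. Which components are planned in which cohort**

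| Item | Cohort 1 | Cohort 2 |
|---|---|---|
| Composite as endpoint, Protocol 7.6 | not listed | listed |
| Composite as endpoint, SAP 3.2.2 | listed | listed |
| Evaluation at visits, Protocol 7.7 and 7.7.2 | not planned | planned |
| MELD score, Protocol 7.7.7 and SAP 3.2.2 | not planned | planned |
| Recording of liver complications in follow-up after week 52, Protocol 5 and SAP 4 | yes | yes |

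MELD is the component clearly unplanned in cohort 1. Deaths, transplants, HCC and hospitalisations may reach the database by other recording.

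**2. Shortfall in the pooled absolute risk**

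Let r1 and r2 be the true composite risks in cohorts 1 and 2, and m the share of cohort 1 events missed. Assume that cohort 2 events are fully seen. The fair reference is the true pooled risk, so

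relative shortfall = 160·r1·m / (160·r1 + 100·r2).

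The values of r1, r2 and m are assumptions. With r2 = 10%:

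| r1 | m | Calculation | Shortfall |
|---|---|---|---|
| 3% | 1 | 4.8 / 14.8 | 32% |
| 3% | 0.3 | 1.44 / 14.8 | 10% |
| 1% | 1 | 1.6 / 11.6 | 14% |
| 1% | 0.3 | 0.48 / 11.6 | 4% |
| 0% | any | 0 / 10 | 0% |

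**3. Distortion of the crude high-risk versus lesser-risk ratio**

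Let p1 and p2 be the shares with PDRpeak at or below 20 %/h, and suppose that MBT has no effect within either cohort. Then

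- high-risk group: [160·p1·r1·(1−m) + 100·p2·r2] / (160·p1 + 100·p2)
- lesser-risk group: the same with 1−p1 and 1−p2 in place of p1 and p2.

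Assume p1 = 20%, p2 = 50% and r1 = r2 = 5%. At m = 0.5 the risks are (0.8 + 2.5)/82 = 4.02% and (3.2 + 2.5)/178 = 3.20%, a ratio of 1.26 where the truth is 1. At m = 0 the ratio is 1.00, and at m = 1 it is 2.17. With p1 = p2 it stays at 1.00 for every m.

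If r1 = 3% and r2 = 10% instead, the ratio is already 1.46 at m = 0, through case mix alone. Missed events raise it to 1.72 at m = 0.5 and 2.17 at m = 1. Under these assumptions, restricting the analysis to cohort 2 or stratifying by cohort returns the within-cohort ratio whatever m is.

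**4. Scale in events**

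The SAP expects fewer than 80 subjects with valid baseline and post-treatment MBT. If 79 subjects split as planned, about 79 × 160/260 = 49 are in cohort 1 and 79 × 100/260 = 30 in cohort 2. At r1 = 3% and r2 = 10%, that is about 1.5 and 3.0 expected events.

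**The case against.** The strongest reply is that cohort 1 events will be seen anyway. Protocol 3.2 says that all liver-related outcome events will be captured, both studies have safety and efficacy visits every 4 to 8 weeks, and complications are recorded in follow-up. This stands in part: other recording may supply most components, and the schedules of the parent studies are not in these documents. But the Protocol 3.2 sentence refers to section 7.7.2, which is limited to cohort 2. The follow-up statement concerns the time after week 52. Neither mentions MELD in cohort 1.

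A second reply is that SAP 5.1 excludes subjects missing the clinical outcome, and that 3.2.2 collects measures where available. But 5.1 does not say whether a cohort 1 subject without MELD counts as missing. If so, the combined analysis reduces to cohort 2. If not, the gap remains.

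A third is that the consequence is limited: nothing is formally tested, each cohort is reported separately, and small sites are grouped within cohort, so the site term in the Cox model may absorb part of the difference. This is fair for the hazard ratio. It does not help the pooled Kaplan-Meier plot, the unstratified log-rank test or the crosstab.

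Nor did the SAP create the mismatch alone. The protocol's own objectives already covered both cohorts, although its endpoint list did not.

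**Conclusion.** The concern holds as an inconsistency in ascertainment that the SAP should resolve before data access. As written, at least the MELD component is not planned in cohort 1, while cohort 1 subjects without a recorded event are censored as event-free in a lead population that pools both cohorts. Under the assumed risks the pooled absolute risk is understated by between 0% and about 32%. The crude MBT comparison is inflated only if low PDRpeak is commoner in cohort 2, which Protocol 3.2 makes plausible because it links advanced disease with low MBT values.

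Three stronger readings are tempting but unsupported.

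- A reader might infer that pooled risks are about 62% too low, from 160/260 = 61.5%. That takes the cohort 2 risk as the true pooled risk. Part or all of that gap may be a truly lower risk in stage 3 fibrosis.
- A reader might take 160:100 as the split of the MBT subjects. Those are the sizes of the parent studies, which include Japan, where no MBT was done. The sub-study was opt-in, and its split is not given.
- A reader might infer that no cohort term could help. A cohort stratum could largely repair the hazard ratio, but not the pooled absolute risks.

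**What to change.** - In SAP 3.2.2, return the composite to the cohort 2 list. In 3.1.2 and 8.4.2.1, make the cohort 2 run the lead for the Cox model, Kaplan-Meier plot and crosstab.
- List cohort 1 deaths and liver complications descriptively.
- If a pooled analysis is kept, label it supportive, use a common composite without MELD, and stratify by cohort.
- In SAP 5.1, state that cohort 1 subjects count as missing the composite that contains MELD.
- Reconcile the MELD component with Protocol 7.7.2, which also requires a rise of at least 2 points from baseline; SAP 3.2.2 does not mention it.

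The cost is SAP wording. Section 2 allows amendments before the companion sponsor accesses the data, which it expects between July and November 2021, and the per-cohort runs are already planned. The downside is a smaller lead analysis, about 30 of 79 subjects if the planned split applied. Any cohort 1 events would move to the descriptive and supportive outputs.

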| Secondary Efficacy Endpoint measures: | 
In order to assess the correlation of MBT with other measures of liver disease, the following endpoint measures will be collected:
 
For all study cohorts: MBT results for each MBT visit (day 1, week 24, week 48) as well as changes in MBT results (CPDR30/PDR peak or other breath test parameters).
 
The other measures of liver disease that will also be collected in this study are as follows:
 
Liver Fibrosis stage and NAS as determined by Liver Biopsy, PDFF as determined by MRI where available, Liver Stiffness as determined by MRE where available, Serum Biomarker Pro-C3.
 
Additional measures for cohort 2 include: MELD and CTP scores, Liver Stiffness as determined by Fibroscan® Elastography, Liver-related Clinical Outcome defined as the first occurrence of any one of the following: all-cause mortality, MELD score ≥ 15, liver transplant, hepatocellular carcinoma (HCC), ascites requiring medical intervention, hospitalization (≥ 24 hours) for onset of variceal bleeding, hepatic encephalopathy and spontaneous bacterial peritonitis.
 |
| Statistical Analysis: | 
The ¹³C-Methacetin Breath Test will primarily be assessed for its ability to measure the effect of BMS-986036 on the metabolic capacity of the liver at 24-week intervals during the Double-Blind Treatment Period as compared to placebo, by modelling the MBT results and the change in its value from previous visits, including the baseline MBT, to each of the subsequent visits using Mixed Effect Model for Repeat Measurements (MMRM).
 
Secondary endpoints will be assessed through Cox and Linear regressions in order to test for prognostic value and correlations between MBT and other Liver related outcomes and measures.
 |

| | |
|---|---|
| Exalenz Bioscience Ltd. | Last update: February 20, 2018 |
| Study Title: Companion protocol for the ¹³C-Methacetin Breath Test (MBT) for use in Bristol-Myers Squibb phase 2b studies for BMS-986036 (PEG-FGF21), under Protocols MB130-068 and MB130-069 | Protocol: BMS-EX-0118 Version: 1.0 |
| Document No: CSP000002 | Page 14 of 38 |

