All liver-related clinical outcome events will be captured in this study (see section 7.7.2). One of this study's aims is to show the ability of the ¹³C-methacetin breath test to identify Subjects at risk for decompensation and to determine the effect of BMS' study drug BMS-986036 on the metabolic capacity of the liver at 24-week intervals during the Double-Blind Treatment Period compared to placebo.

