SAP for Protocol BMS-EX-0118: Companion protocol for the ¹³C-Methacetin Breath Test (MBT) for use in Bristol-Myers Squibb phase 2b studies for BMS-986036 (PEG-FGF21), under Protocols MB130-068 and MB130-069	Document Version: 1.0
Document Nº: CSD00114	Page 8 of 21

for the study will be descriptive by nature. No formal statistical testing will be performed. Nominal p-values from statistical tests will be reported for supplementary information.

When differences exist in methods, descriptions or explanations provided in the protocol and this SAP, the SAP prevails.

Since this study is a companion to a pharmaceutical company's study, the data management for the main study can independently determine as to when a data freeze or a data lock shall be performed. Therefore, for the Exalenz companion protocol purposes, any amendments to the SAP will be made prior to Exalenz independently accessing the data from the database freeze or lock, if available. In case additional analyses not described in the final SAP or deviations from the final SAP are required, they will be documented in the Clinical Study Report (CSR).

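### The MELD component of the liver-related outcome has two definitions that part at a baseline MELD of 14; read literally, the prevailing SAP text counts a one-point rise or an unchanged score as deterioration.

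*SAP*

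**What the plan says.** The composite is used in the prognostic analysis of SAP 8.4.2.1. There, time from the Day 1 breath test to the first event enters a Cox model, a Kaplan-Meier plot and a table of events by breath-test group.

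- **SAP 3.2.2** defines it as "Liver-related Clinical Outcome defined as the first occurrence of any one of the following", with the list "all-cause mortality, MELD score ≥ 15 , liver transplant, hepatocellular carcinoma (HCC" and the remaining complications. No change from baseline is required for MELD.
- **Protocol synopsis** (secondary endpoint measures) uses the same bare threshold: "all-cause mortality, MELD score ≥ 15, liver transplant, hepatocellular carcinoma (HCC". **Protocol 7.6** repeats it.
- **Protocol 7.7.2** itemises the events under the sentence "Cohort 2 will be evaluated for the following liver-related clinical outcome events at every visit during the treatment periods". Its MELD line has the same threshold of 15 but adds "with at least a 2-point increase from Baseline".
- **Protocol 3.2** points to that section: "All liver-related clinical outcome events will be captured in this study (see section 7.7.2".
- **SAP section 2** sets the order of precedence: "When differences exist in methods, descriptions or explanations provided in the protocol and this SAP, the SAP prevails".

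SAP 8.4.2.1 does not restore the two-point condition.

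**The concern.** The secondary objective in SAP 3.1.2 is the prognostic value of the breath test for liver disease deterioration, and the composite is the measure of deterioration. A bare threshold records where a subject's MELD stands. A threshold with a required rise records that it has worsened. For a subject who enters close to 15 or above it, these are different events.

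The definition decides who has an event and when, so it can alter the hazard ratio, the survival curves and the crosstab. A reader of the results could not tell which rule produced the counts. It should be settled before the data are seen, because a rule chosen later could be chosen knowing which events it adds or removes.

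**Working it through.** **Inputs.** Let *b* be the baseline MELD and *f* a follow-up MELD, both whole numbers. The threshold of 15 is in all four places. The rise of at least 2 is in Protocol 7.7.2 only.

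**Rules.**
- SAP 3.2.2, read literally: event if *f* ≥ 15.
- Protocol 7.7.2: event if *f* ≥ 15 and *f* − *b* ≥ 2, that is *f* ≥ max(15, *b* + 2).

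**Comparison.**

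| Baseline *b* | SAP trigger | 7.7.2 trigger | Scores that are events under the SAP only |
|---|---|---|---|
| 12 | 15 | max(15, 14) = 15 | none |
| 13 | 15 | max(15, 15) = 15 | none |
| 14 | 15 | max(15, 16) = 16 | 15 |
| 15 | 15 | max(15, 17) = 17 | 15, 16 |
| 16 | 15 | max(15, 18) = 18 | 15, 16, 17 |

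The rules differ only when *b* + 2 > 15, that is from *b* = 14 upward. The scores in dispute then run from 15 to *b* + 1. Enumeration over scores 6 to 40 gives the same pattern.

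**Particular cases.**
- 13 to 15 (+2) and 14 to 16 (+2): events under both rules.
- 14 to 15 (+1): event under the SAP only.
- 15 to 15 (0) and 16 to 15 (−1): events under the SAP only, although the score has not risen.

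**A Day 1 score of 15 or more.** Protocol 7.7 assesses outcome events from Day 1. SAP 8.4.2.1 computes time as event date minus Day 1 breath-test date plus 1. A Day 1 MELD of 15 or more could then be an event at time 0 + 1 = 1 day, unless first occurrence is read as new onset, which the SAP does not state. Under Protocol 7.7.2 with Day 1 as baseline this cannot happen: the rise is 0, which is less than 2.

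**Which baseline.** SAP 8.2 sets baseline as the Day 1 value, and SAP 3.1.2 and Protocol 7.2 both compare MELD with study Day 1. Protocol 9.6.1 takes the last valid value before treatment, which is normally the same score if the Day 1 sample precedes dosing.

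**How many subjects.** This cannot be computed. The documents give no MELD entry limit for MB130-069, no baseline MELD distribution and no count of cohort 2 subjects with a breath test. The expected figure below 80 in SAP section 2 covers both cohorts and counts subjects with valid baseline and post-treatment tests. The modified efficacy set requires only a successfully performed test, so that figure does not bound the Cox analysis. If every cohort 2 subject entered with MELD 13 or less, the number affected is zero.

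**The case against.** The strongest reply is that SAP 3.2.2 is shorthand. It nearly repeats the summary sentence of the synopsis and Protocol 7.6, which already stands beside the itemised list in Protocol 7.7.2. It also condenses other items, running three separate hospitalisation lines into one phrase. On this view the SAP is silent on the two-point condition and does not revoke it, and the precedence rule is not engaged. This reading is plausible. A reader might infer that the SAP counts 14 to 15 however it is read; the documents do not support that, and the point holds for the literal reading. But nothing in the SAP tells the analyst to use the shorthand reading, and the precedence rule points the other way.

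Second, the study relies on data from the parent studies. If events arrive already flagged under a rule like that of 7.7.2, no count may change. That also stands, but the SAP would then misdescribe the events analysed.

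Third, the effect may be nil, and the analyses are descriptive. The low impact is accepted. Descriptive status removes formal testing; it does not remove the need to define an event.

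Two other inferences should be resisted. Counting the scheduled MELD visits does not measure impact, because each subject contributes at most one first event and event-free subjects are censored at the Final Treatment visit. Nor is the baseline an open conflict: it is largely settled as Day 1. Only parent-study flags, whose baseline is not shown, could differ.

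**Conclusion.** The inconsistency is real, and it lies within the protocol as well as between protocol and SAP. On a literal reading, the controlling text counts a 14-to-15 rise, and an unchanged or falling score that stays at 15 or more, as deterioration; Protocol 7.7.2 does not. The difference is confined to baseline MELD of 14 or more.

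The size is low: a secondary, descriptive analysis, a component scored in cohort 2 only, and an unknown number of subjects that may be zero. Protocol 3.2 reports that the breath test correlates with MELD, so a reader might infer that the literal rule favours the test by adding events among low breath-test values. That is possible, but without baseline MELD data neither the direction nor the size of any effect can be shown.

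The conclusion assumes whole-number MELD scores, Day 1 as baseline, and events derived as SAP 3.2.2 is written. It is worth acting on because the rule as written departs from the plan's own target and the correction is cheap.

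**What to change.** Amend SAP 3.2.2 and 8.4.2.1 while the SAP still allows it: "any amendments to the SAP will be made prior to Exalenz independently accessing the data". Deviations can also be documented later in the study report, but a definition fixed in advance is preferable.

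1. State one analysis definition of the MELD component and reconcile it with the synopsis, Protocol 7.6 and Protocol 7.7.2. Of the wordings in the documents, that of 7.7.2 fits the deterioration target.
2. Apply it against the Day 1 MELD, so that a score already at 15 or more on Day 1 is not itself an event.
3. State whether events are taken as flagged by the parent studies or re-derived from visit MELD scores. If flagged events are used, give the rule and baseline behind the flag.
4. Report the number of subjects whose only event is the MELD criterion.

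The cost is a few lines of SAP text. Day 1 and visit MELD scores are already collected in cohort 2, so no new data are needed. The downside is that fewer events may be counted.
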